4.3.3 Safety Population

The safety population will be used to report the summaries of the adverse events that are not constituents of the secondary endpoints. The safety population is defined as all randomised patients who underwent induction of general anaesthesia for surgery, with groups defined as randomised.

4.4 *Observational Period*

The observational period for the study will be from the date of surgery to 1 year.

5 *DEMOGRAPHIC AND BASELINE CHARACTERISTICS*

To summarise the randomisation process, participant demographic and baseline clinical characteristics will be summarised descriptively by randomised group. These variables will also be summarised by randomised group within the predefined study-centre groups. Summaries will include frequencies and percentages for categorical data and means, medians, ranges, standard deviations and inter-quartile ranges as appropriate for continuous data. These baseline summaries will include the following variables:

- Age
- Weight
- Sex
- Ethnicity
- ASA physical status
- Charlson score
- WHODAS score
- Cancer diagnosis
- Emergency/elective surgery
- Surgery type
- Haemoglobin
- Albumin
- Creatinine
- Surgical duration

These data will be examined for any imbalances between randomised treatments. If potentially confounding influences are identified, appropriate statistical adjustment will be used to mitigate these in sensitivity analyses and these will be reported and discussed in any reports or publications arising from the study. No formal hypothesis testing will be conducted on these baseline variables.

6 PARTICIPANT DISPOSITION

A flowchart will be produced showing the flow of participants throughout the study. The numbers of participants approached, screened and consented will be summarised. Those who are screened and consented but not randomised will also be summarised.

Any participants who are randomised but do not have surgery will be individually listed with explanation, by randomised group.

Any patients inappropriately randomised (subsequent to randomisation are found to violate inclusion/exclusion criteria) will also be individually listed with their inclusion or exclusion violations.

7 STUDY MEDICATION AND CONCOMITANT THERAPY

7.1 Compliance

To evaluate the degree of compliance with randomised BIS target, tabular summaries of achieved BIS values will be presented by randomised group.

The association between achieved target BIS value and all outcomes will be tested using exploratory analyses as outlined below.

7.2 Physiological data

Bispectral index (BIS), mean arterial pressure (MAP) and minimum alveolar concentration (MAC) of the volatile anaesthetic agent for each patient during anaesthesia will be recorded digitally whenever possible. Analysis will be from first BIS<50 after commencing anaesthesia or 5 minutes after anaesthesia induction if BIS<50 not achieved in that time period, until switch-off of volatile anaesthetic at the end of the case. Mac will not be adjusted for age.

BIS recordings will be visually inspected, obvious artefacts removed and then cleaned by removing all data when the signal quality index is less than 50%, when signal quality is available. Mean BIS for each individual patient will then be calculated.

Mean MAC during this time period will also be calculated for each patient.

Mean MAP will be calculated for each patient during this time period. In addition mean of the target MAP range will be calculated. Mean $(MAP - MAP_{target})$ will then be calculated to establish how well the patient has tracked.

These values will be reported in the ITT summaries as mean and standard deviation for each group

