9 CONFOUNDING

Relative hypotension associated with deep anaesthesia is suspected to be a confounding factor that may be the explanation for observed mortality difference in the published evidence to date. The BALANCED study design has attempted to mitigate these effects (via the use of vasopressors and inotropes) but achieved MAP may still confound the comparison between randomised groups. A multivariate analysis of 1 year mortality will be undertaken using Cox proportional hazards regression in which randomised group, study-centre-group, the use of vasopressors/inotropes and achieved MAP are included as covariates.

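### The signed mean of MAP minus target in section 7.2 measures average bias, not how closely MAP was held within a case; a deviation measure and a below-range measure should be added

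*Combined protocol and SAP*

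**What the plan says.** Section 7.2 (Physiological data) sets an analysis window that ends when the volatile agent is switched off. Its start is given as: "Analysis will be from first BIS<50 after commencing anaesthesia or 5 minutes after anaesthesia induction if BIS<50 not achieved in that time period".

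Three MAP quantities follow:

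- the patient's average: "Mean MAP will be calculated for each patient during this time period";
- a single reference value: "In addition mean of the target MAP range will be calculated";
- the tracking measure: the mean of MAP minus that reference value, printed with ordinary parentheses, "will then be calculated to establish how well the patient has tracked".

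On reporting, the section says: "These values will be reported in the ITT summaries as mean and standard deviation for each group".

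Section 9 (Confounding) explains why MAP matters to the trial: "Relative hypotension associated with deep anaesthesia is suspected to be a confounding factor". It plans a Cox model of one-year mortality in which "the use of vasopressors/inotropes and achieved MAP are included as covariates", alongside randomised group and study-centre group. Section 9.1 uses achieved MAP again in its exploratory multivariable models. The only summary of MAP level that the plan defines is the mean in section 7.2. It specifies no absolute or squared deviation, no time or area below the range, and no lowest MAP.

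**The concern.** Tracking concerns how close pressure stayed to target during the case. A mean that keeps its sign answers a different question: whether pressure was on average above or below target. Highs and lows within a case offset each other, so good and poor control can give the same score. Replacing the range by its midpoint also discards the lower limit, which is what decides whether a reading was below range.

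What is at stake is interpretation. Readers will want to know whether pressure was managed alike in the two arms before attributing a mortality result to anaesthetic depth. The planned summaries can show whether average pressure was alike. They cannot show whether time spent below range was alike.

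**Working it through.** The plan gives no MAP values, no width for the target range and no expected tracking result, so there is no stated figure to reproduce. The check is algebra, followed by hypothetical traces.

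**Inputs from section 7.2.** The metric is the mean of (MAP − T), printed with ordinary parentheses. T is one number per patient, the midpoint of the range. Results are reported as group mean and SD.

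**Assumptions for illustration.** T is fixed during the case. The lower limit lies 10 mmHg below the midpoint. Within-case deviations are as stated below.

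**Step 1: what the metric contains.** For fixed T, mean(MAP − T) = mean(MAP) − T. A numerical check with T = 85 gave −5.879 both ways. The metric is therefore the mean MAP already reported, shifted by a constant for each patient. It adds information on level relative to target, and none on variation within the case.

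**Step 2: three traces with the same score.** Deviations are in mmHg from the midpoint.

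| Trace | Signed mean | Mean absolute deviation | Time below limit | Average shortfall below limit |
|---|---|---|---|---|
| Always at target | 0 | 0 | 0% | 0 |
| Half at −20, half at +20 | 0.5(−20) + 0.5(20) = 0 | 20 | 50% | 0.5 × 10 = 5 |
| 25% at −30, 75% at +10 | 0.25(−30) + 0.75(10) = 0 | 7.5 + 7.5 = 15 | 25% | 0.25 × 20 = 5 |

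**Step 3: the group SD.** The SD is taken over the per-patient means. If every patient in one arm followed the first trace and every patient in the other followed the second, both arms would report mean 0 and SD 0. What cancels inside a patient's mean cannot be recovered from the spread of those means.

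**Step 4: a range of within-case variation.** Take deviations as normal with mean 0 and SD s. The mean absolute deviation is s√(2/π), and the proportion of time below the limit is Φ(−10/s).

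| s (mmHg) | Signed mean | Mean absolute deviation | Time below limit |
|---|---|---|---|
| 5 | 0 | 4.0 | 2.3% |
| 10 | 0 | 8.0 | 15.9% |
| 15 | 0 | 12.0 | 25.2% |
| 20 | 0 | 16.0 | 30.9% |

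**Step 5: what the metric does show.** A patient held 10 mmHg below target throughout scores −10. A shift of a whole arm appears in the same way, as a negative group mean. The mean absolute deviation for that patient is 10, as it would be for one held 10 mmHg above, so it cannot replace the signed mean.

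**The case against.** The best defence is that the sign is useful here. Section 9 is concerned with a directional effect, lower pressure under deeper anaesthesia. A sustained or arm-wide fall would make the signed mean more negative in that arm, and the planned table would show it. This stands, and it is why the signed mean should stay.

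Three further points also stand:

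- Cancellation across patients is not hidden. If some patients run high and others low, the group mean may be near zero but the reported SD widens. Only cancellation within a patient is lost.
- For both arms to score 0 while one spends far longer below range, low readings in that arm must be offset by high ones. Nothing in the documents suggests that deep anaesthesia does this. The figures in steps 2 and 4 show what is possible, not what is expected.
- The metric enters no test. The primary analysis in section 8.1 is a stratified Mantel-Haenszel comparison by randomised group.

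A reader might infer that this metric was the plan's means of detecting hypotension and that it would miss it. The documents support neither step. Section 7.2 gives the purpose as tracking, section 9 does not refer to the metric, and a sustained fall would be seen.

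None of this answers the narrower point: the stated purpose is tracking, and a signed mean cannot measure it.

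**Conclusion.** The concern holds in a limited form. As printed, the section 7.2 metric measures average bias from the midpoint of the range. It cannot establish how closely a patient was held to target or whether MAP stayed within range. Traces with mean absolute deviations of 0, 15 and 20 mmHg, and with 0%, 25% and 50% of the time below an assumed limit, all score 0.

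The algebra needs only a target that is fixed within the patient. The percentages rest on the assumed limit and the assumed variation, because the documents give neither. If absolute-value bars were intended in the expression, the text should say so; direction would then be lost, and position relative to the range would still be missing.

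It would be too strong to conclude that the primary mortality comparison is affected, or that a difference in average pressure between arms would go unnoticed. The practical effect is on interpreting the confounder named in section 9. If achieved MAP in that model, and in section 9.1, is the section 7.2 mean, the adjustment has the same blind spot for intermittent low pressure, although it still captures differences in average pressure.

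**What to change.** Amend section 7.2 before database lock, as section 13 allows:

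1. Keep the signed mean, described as the measure of direction and average bias.
2. Add, per patient and summarised by randomised arm, the mean absolute deviation of MAP from target.
3. Add, per patient and by arm, the proportion of time and the time-weighted area below the lower limit of that patient's own target range.
4. Base statements about tracking on item 2, and statements about hypotension on item 3.
5. State in section 9 which section 7.2 quantity achieved MAP refers to.

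The change is to analysis only. It needs no new data collection and does not alter how pressure is managed. It has two costs. Section 7.2 foresees digital recording only where this can be done, so the new measures cover only patients with usable MAP traces, and the number in each arm should be reported. Section 7.2 also specifies artefact removal and signal-quality cleaning for BIS but not for MAP. Time and area below a limit are sensitive to spurious low readings, so a MAP cleaning rule has to be written, and applied identically in both arms, before these measures are computed.

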8 EFFICACY ANALYSES

8.1 Primary endpoint analyses:

The primary endpoint analysis will compare the primary endpoint, one-year mortality in the intention-to-treat population, using a Mantel-Haenszel Chi-square test, stratified by study-centre groups. The pooled estimate of the odds ratio and 95% confidence interval from this analysis will be used to summarise the statistical comparison.

Supportive analysis of the primary endpoint will compare randomised groups using a stratified log-rank test with results summarised using Kaplan-Meier curves and hazard ratios in which withdrawn participants will be censored at the last date that they are confirmed to be event-free.

A two-tailed p-value < 0.049 will be taken to indicate statistical significance. The primary endpoint will be analysed using the full analysis set i.e. using those individuals who have confirmed outcome status, with groups designated as randomised on the intention-to-treat basis. Sensitivity analyses will also be undertaken with those missing outcome data assigned a poor outcome.

8.2 Secondary efficacy analyses:

The differences between randomised groups will be analysed using stratified Mantel-Haenszel Chi-square tests, stratified by study-centre group and general linear models, as appropriate to the form of the secondary endpoint. The occurrence of MI, cardiac arrest, PE, stroke, cardiac composite, surgical site infection, sepsis, infection composite, awareness, persistent post-operative pain and cancer recurrence within one year post-surgery will be analysed using stratified Mantel-Haenszel Chi-square tests. Supportive analysis of these secondary endpoints will compare randomised groups using a stratified log-rank test with results summarised using Kaplan-Meier curves in which withdrawn participants will be censored at the last date they are confirmed to be event-free. Sensitivity analyses will also be undertaken for these secondary endpoints with those missing outcome data assigned a poor outcome.

ICU stay, hospital stay, days disability-free and alive within one-year post-surgery and WHODAS scores at 30 days and 1 year will be analysed using general linear models with study-centre group and randomised treatment as

fixed factors. If the data do not meet assumptions for parametric analyses, the data will be log-transformed and if this does not achieve adequate normality then the groups will be compared using the Mann-Whitney U non-parametric tests.

The endpoints; infection composite (the composite of secondary endpoints sepsis, surgical site infection) and composite of mortality and cardiac events (mortality MI, cardiac arrest, PE and stroke) will be compared between randomised groups using stratified Mantel-Haenszel Chi-square tests and using a stratified log-rank test with results summarised using Kaplan-Meier curves in which withdrawn participants will be censored at the last date they are confirmed to be event-free.

Standard descriptive statistics including frequencies, percentages, means, medians and ranges will be used to describe the levels for the secondary endpoints. The differences between randomised groups for the secondary endpoints will be summarised using model derived odds ratios and mean differences with 95% confidence intervals.

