3.3 Secondary Objectives

The secondary efficacy objective is:

- To compare secondary efficacy/safety endpoints to one-year between randomised BIS target groups 50 and 35.

The secondary endpoints are:

1. **MI:** According to the 3rd Universal Definition (Thygesen K, Alpert JS, Jaffe AS, et al. Third universal definition of myocardial infarction. Circulation 2012;126:2020-35.), defined by either of:
 - A typical rise of troponin OR a typical fall of an elevated troponin OR a rapid rise and fall of CK-MB, PLUS one of the following: i) ischaemic symptoms, ii) pathological Q waves, iii) ECG changes indicative of ischaemia, iv) coronary artery intervention, and/or v) new or presumed new wall motion abnormality on echo or mibi scan; OR
 - Autopsy findings of MI
2. **Cardiac arrest:** Defined as a successful resuscitation from either documented or presumed ventricular fibrillation or sustained ventricular tachycardia or asystole
3. **Pulmonary embolism:** high probability VQ scan or documented on pulmonary angiogram or spiral CT, or at autopsy
4. **Stroke:** cerebral infarction or haemorrhage on CT or MRI scan, or new neurological signs (paralysis, weakness or speech difficulties) lasting more than 24 hours or leading to earlier death
5. **Sepsis:** using Centers for Disease Control and Prevention with National Healthcare Safety Network criteria: - SIRS plus infection (positive blood culture or purulence from any site)
6. **Surgical site infection:** if associated with purulent discharge and/or a positive microbial culture
7. **MI, cardiac arrest, PE and stroke:** the composite of secondary cardiac endpoints 1 to 4.
8. **Total ICU stay:** including initial ICU admission and readmission time
9. **Hospital stay:** from the start (date, time) of surgery until actual hospital discharge.

10. **Awareness:** Questioning for evidence of awareness under anaesthetic using the modified Brice questionnaire administered once in hospital, preferably on the day following surgery, and again on day 30.
11. **WHODAS score:** pre-operative, day 30 and 1 year
12. **Disability free survival:** disability-free survival up to 1 year: survival and freedom from new-onset disability, the latter defined as a 4-point or greater increase in the WHODAS score. Disability will be assessed by the participant, but if unable then we will use the proxy's report. The date of onset of new disability will be recorded.

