13. **Persistent post-operative pain:** pain over the surgical site, for at least three months after surgery, that cannot be explained by other causes, such as disease recurrence or a pre-existing pain syndrome
14. **Cancer recurrence:** defined as clinical radiological or pathological evidence for recurrence of the tumour either at the local or a distant site.
15. **Adverse Events:** all adverse events collected during the study categorised by preferred term.

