4.2 Sample size calculation

One year all-cause mortality is expected to be ~10% based on the findings of Leslie et al. and Gurman et al. The relative risk reduction in mortality in the BIS=50 group is expected to be 20%. A power analysis using $p_1=0.10$ and $p_2=0.08$ indicates that $N=3250$ patients are required in each group, $1-\beta=0.8$, $\alpha=0.049$. The alpha level is reduced to allow for the single interim analysis.

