12 MISSING DATA

In the event that a patient withdraws (discontinues the study or is lost to follow-up) from the study, information on their survival and secondary endpoint status at the time they are withdrawn will be included in the relevant endpoint analysis. Sensitivity analyses will also be undertaken with those missing outcome event data will be assigned a poor outcome. There will be no imputation of the ICU stay, hospital stay, days disability-free and alive within one-year post-surgery and WHODAS data at 30 days and 1 year.

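### Section 8.2 plans Kaplan-Meier curves for endpoints that exclude death without saying how event-free deaths are handled, and extends the method to awareness and persistent pain, where it adds no time information

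*Combined protocol and SAP*

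**What the plan says.** Section 8.2 names eleven binary endpoints for stratified Mantel-Haenszel testing on occurrence within one year: MI, cardiac arrest, PE, stroke, the cardiac composite, surgical site infection, sepsis, and then "infection composite, awareness, persistent post-operative pain and cancer recurrence within one year post-surgery will be analysed using stratified Mantel-Haenszel Chi-square tests". The next sentence applies to all eleven: "Supportive analysis of these secondary endpoints will compare randomised groups using a stratified log-rank test with results summarised using Kaplan-Meier curves". A later paragraph of 8.2 repeats the method for the infection composite and for the mortality-plus-cardiac composite.

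The censoring rule is that "withdrawn participants will be censored at the last date they are confirmed to be event-free". Section 12 explains withdrawal: "In the event that a patient withdraws (discontinues the study or is lost to follow-up) from the study". Sections 4.3.1 and 4.3.2 describe it the same way. Death is not part of that description. The SAP nowhere mentions competing risks, cumulative incidence or cause-specific hazards.

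Among these endpoints only the exploratory mortality-plus-cardiac composite (section 3.4) includes death from any cause. In section 3.3, MI and PE may be established at autopsy and stroke may be fatal, so some deaths are themselves events.

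Section 3.3 assesses awareness under anaesthetic by a questionnaire "administered once in hospital, preferably on the day following surgery, and again on day 30". It defines persistent pain as "pain over the surgical site, for at least three months after surgery". It states that an onset date is recorded for new disability, and makes no such statement for awareness or pain.

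**The concern.** A patient who dies without, say, a recurrence can no longer have one. Kaplan-Meier treats a censored patient as still able to have the event later. If deaths are censored, one minus the curve therefore estimates incidence as if nobody died, which is higher than the proportion of patients who actually have the event. One report could then show two different one-year incidences for the same endpoint: a lower one in the Mantel-Haenszel table and a higher one on the curve.

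Death is also the primary endpoint and is expected to differ between the arms, so the gap need not be the same in both.

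For awareness and persistent pain the question is different: whether time to event carries any information at all. Awareness arises during the anaesthetic, and persistent pain cannot be established before three months.

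**Working it through.** **Inputs from the SAP.** Section 4.2 expects one-year mortality of 10%, falling to 8% in the BIS 50 group. Section 4.4 sets follow-up from surgery to one year. As a check that these are the plan's working rates, the usual two-sided formula with pooled variance gives

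n = [1.9686·√(2·0.09·0.91) + 0.8416·√(0.10·0.90 + 0.08·0.92)]² / 0.02² = 3233 per group,

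against the stated 3250 (power 80.2% at 3250). The plan's figure reproduces.

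**Assumptions.** The SAP gives no rates or timing for the secondary endpoints, so both are assumed below. Deaths are taken to occur at a constant hazard d = −ln(1 − D), which is 0.0834 for D = 8% and 0.1054 for D = 10%. All of D is treated as competing, and the death hazard is taken to be the same before and after an event.

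**Formulas.** Let events occur at rate r between times s and e (in years), with cumulative hazard H = r(e − s).

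- True incidence: CIF = exp(−d·s) × r/(r + d) × [1 − exp(−(r + d)(e − s))]
- Kaplan-Meier with deaths censored: 1 − KM = 1 − exp(−H)

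**Worked case.** Spread over the year, H = −ln(0.90) = 0.1054 and D = 10%: CIF = 0.5 × (1 − 0.90 × 0.90) = 9.50%; 1 − KM = 10.0%; ratio 1.053.

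| Assumed event timing | H | 1 − KM | CIF, D = 8% | CIF, D = 10% | Relative excess |
|---|---|---|---|---|---|
| First 30 days | 0.10 | 9.52% | 9.48% | 9.48% | 0.3% to 0.4% |
| Spread over the year | 0.1054 | 10.0% | 9.60% | 9.50% | 4.2% to 5.3% |
| Months 6 to 12 | 0.10 | 9.52% | 8.94% | 8.80% | 6.4% to 8.2% |
| About month 12 only | 0.20 | 18.13% | 16.69% | 16.33% | 8.6% to 11.0% |

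For events spread over the year, the relative excess hardly depends on the event rate. For true incidences from 1% to 20% it is 4.1-4.2% at 8% mortality and 5.1-5.4% at 10%.

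**Between arms.** With the same event hazard in both arms and 10% v 8% mortality, the second row gives true incidences of 9.50% v 9.60%, while both Kaplan-Meier curves read 10.0%. At a higher assumed hazard (H = 0.22) the true incidences are 18.8% v 19.0%, and both curves read 19.7%. The between-arm distortion is 0.1 to 0.2 percentage points.

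**Awareness and persistent pain.** If awareness is dated to surgery, all events share one time point and the stratified log-rank test reduces to the Mantel-Haenszel test already planned. If it is dated to the questionnaire, the time axis shows when patients were asked. The persistent-pain curve stays flat until the three-month threshold and then steps. In each case the one-year proportion already carries the information.

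**The case against.** The strongest reply is that the SAP never says deaths are censored. If patients who die event-free were kept at risk to one year, one minus Kaplan-Meier would equal the cumulative incidence. A reader might infer that the planned curves are biased as written; the text supports only that the rule is missing. The reply does not dispose of the point, however. Keeping deaths at risk is not the usual default, and the plan does not ask for it.

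Several other points stand and limit the finding.

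- These analyses are supportive. Incidence is already reported as frequencies, percentages and odds ratios, so the main results do not depend on the curves.
- A log-rank test that censors deaths is a valid comparison of cause-specific hazards. The fault would lie in reading the curves as incidence, not in the test.
- For perioperative events concentrated in the first weeks, such as surgical site infection, the excess is close to zero.
- Autopsy-confirmed MI or PE and fatal stroke are events, so the competing mortality for those endpoints is below the 8% to 10% used here, and the excess is smaller.

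A reader might also infer that the awareness and pain curves are meaningless, or that awareness can be dated only by the interview. The documents support neither. Awareness can be dated to surgery, whose start section 3.3 uses to time hospital stay, and the data collection forms are not among the documents. The supportable statement is that the analysis is redundant.

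**Conclusion.** The concern holds as a gap in specification with a small, systematic consequence. Section 8.2 does not say how event-free deaths enter the supportive time-to-event analyses of endpoints that exclude death. Under the usual default the curves overstate one-year incidence and disagree with the Mantel-Haenszel proportions even when nobody withdraws.

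The sizes in the table rest on the plan's mortality, a constant death hazard and assumed event timing. They matter chiefly for cancer recurrence, the endpoint most likely to occur late. It would be wrong to conclude that any primary or main secondary result is unsound: none of those tests changes. For awareness and persistent pain, the log-rank and Kaplan-Meier analysis adds no time information to the Mantel-Haenszel test. This is a worthwhile improvement at almost no cost, not a serious defect.

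**What to change.** Amend section 8.2 before database lock, as section 13 allows.

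1. For MI, cardiac arrest, PE, stroke, the cardiac composite, sepsis, surgical site infection, the infection composite and cancer recurrence, replace Kaplan-Meier with cumulative incidence curves (Aalen-Johansen), treating death as a competing event. State that deaths meeting an endpoint definition (MI or PE at autopsy, fatal stroke) count as events and that other deaths compete.
2. Keep the stratified log-rank test for these endpoints, and label it a comparison of cause-specific hazards.
3. Keep Kaplan-Meier for mortality and for the mortality-plus-cardiac composite.
4. Drop the log-rank and Kaplan-Meier analysis for awareness and persistent pain, and rely on the Mantel-Haenszel test.
5. If persistent pain is also shown among patients alive at three months, keep that display descriptive. It conditions on survival after randomisation, which the trial expects to differ by arm, so it needs a survivor-selection caveat.

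The cost is a few sentences of SAP text and standard software output. Death dates and event dates are already needed for the planned curves, so no new data are required, and confirmatory testing is untouched.

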9.1 Additional analyses

- Additional analyses of efficacy endpoints will be undertaken using the PP participant population and including the intermediate BIS group 40 to 45.
- Efficacy endpoints will be summarised by randomized group within categories for age, ASA, surgery type, centre, use of vasopressors/inotropes and anesthetic duration (quartiles). These results will be summarized using forest plots and the consistency of the difference between randomised groups tested using interaction terms within Cox-regression and general linear models as appropriate.
- Multi-variate analyses will be used to explore the independent and combined effects of randomised treatment, age, ASA, surgery type, study centre-groups, anesthetic duration, the use of inotropes, achieved MAP and achieved BIS group on the efficacy endpoints.

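### The WHODAS comparisons at 30 days and 1 year leave out the scheduled pre-operative WHODAS score, so they are valid but less precise than the data allow

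*Combined protocol and SAP*

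**What the plan says.** Section 3.3, item 11, schedules the WHODAS score "pre-operative, day 30 and 1 year". Section 5 includes it in the baseline list.

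For the two follow-up scores, section 8.2 says that "WHODAS scores at 30 days and 1 year will be analysed using general linear models with study-centre group and randomised treatment as" fixed factors. If parametric assumptions fail, the data are log-transformed. If that also fails, "the groups will be compared using the Mann-Whitney U non-parametric tests", which uses neither the baseline score nor centre group.

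Baseline WHODAS, or baseline data in general, appears in these other places:

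- Section 5: "participant demographic and baseline clinical characteristics will be summarised descriptively by randomised group". It adds: "If potentially confounding influences are identified, appropriate statistical adjustment will be used to mitigate these in sensitivity analyses".
- Section 9.1: the exploratory multivariable models cover "randomised treatment, age, ASA, surgery type, study centre-groups, anesthetic duration, the use of inotropes, achieved MAP and achieved BIS group". Pre-operative WHODAS is not named.
- Section 3.3, item 12: disability-free survival combines survival with freedom from new disability, "the latter defined as a 4-point or greater increase in the WHODAS score".

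Section 12 states: "There will be no imputation of the ICU stay, hospital stay, days disability-free and alive within one-year post-surgery and WHODAS data", with reference to the 30-day and 1-year scores.

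**The concern.** A score from the same instrument, taken in the same patient before surgery, would normally be among the best predictors of the follow-up score. When it is left out, variation in pre-existing disability stays in the error term, apart from any part that centre group absorbs. Standard errors and confidence intervals are then wider than they need to be.

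WHODAS is a patient-centred secondary outcome. Section 8.2.1 applies Holm-Bonferroni over ten secondary measures, so if WHODAS is one of them its threshold could be as strict as 0.05/10 = 0.005. Section 8.2.1 does not list the ten, so its place among them is an inference.

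**Working it through.** **The plan's own figure.** The only computed design figure is in section 4.2: 3250 per group for mortality of 0.10 against 0.08, 80% power, alpha 0.049 (two-tailed, section 8.1). With pooled variance and no continuity correction:

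n = [1.969 × √(2 × 0.09 × 0.91) + 0.842 × √(0.10 × 0.90 + 0.08 × 0.92)]² / 0.02² ≈ 3233 per group.

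That agrees with 3250, at which power is 80.2%. The figure concerns mortality and is unaffected by this point. No target difference, SD or correlation is given for WHODAS.

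**Does another section supply the covariate?** No.

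- The section 5 adjustment depends on an imbalance being seen and is confined to sensitivity analyses. Adjustment for a prognostic baseline gains precision even when the groups are balanced.
- The section 9.1 list omits pre-operative WHODAS. It also contains terms fixed only after randomisation (achieved MAP, achieved BIS group, inotrope use, anaesthetic duration), so those models could not replace a baseline-adjusted treatment comparison.
- Section 3.3, item 12, uses change from baseline for a different endpoint.

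**Size of the loss.** For n per group, outcome SD σ and baseline/follow-up correlation r (within centre group):

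- variance of the difference, unadjusted: 2σ²/n
- variance of the difference, adjusted: 2σ²(1 − r²)/n

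The variance falls by r², the standard error is multiplied by √(1 − r²), and the gain equals having 1/(1 − r²) times as many patients. These ratios do not depend on n.

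**Illustration in power.** Assume a difference of 0.06 SD and 3000 per arm; neither figure is in the documents. Unadjusted, the expected z is 0.06 × √(3000/2) = 2.32. Adjusted, it is 2.32/√(1 − r²); at r = 0.5 this is 2.32/0.866 = 2.68. Power is Φ(z − 1.960) at two-sided 0.05 and Φ(z − 2.807) at two-sided 0.005.

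| r (assumed) | Variance cut | SE factor | Patient equivalent | Power at 0.05 | Power at 0.005 |
|---|---|---|---|---|---|
| not adjusted | – | 1 | 1 | 64% | 31% |
| 0.3 | 9% | 0.954 | 1.10 | 68% | 36% |
| 0.5 | 25% | 0.866 | 1.33 | 77% (76.5%) | 45% |
| 0.7 | 49% | 0.714 | 1.96 | 90% | 67% |

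**The same gain as a detectable difference** (80% power, 3000 per arm, r = 0.5): at 0.05, (1.960 + 0.842) × √(2/3000) = 0.072 SD falls to 0.063 SD; at 0.005, 0.094 SD falls to 0.082 SD.

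**The case against.** The best case for leaving the plan alone is that nothing in it is invalid and the trial is already large. It is sized on mortality, and WHODAS is one of 15 listed secondary endpoints. At r = 0.5 adjustment improves the detectable difference by only about 0.01 SD. With no WHODAS target in the documents, nothing shows that this would change a conclusion. The power example sits where power is sensitive to small changes, and at 0.005 the comparison stays underpowered at r = 0.5. All of this stands, and it limits the weight of the point. It is not a reason to discard a score that is scheduled anyway.

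Three stronger readings are tempting, and the documents do not support them.

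- *The unadjusted comparison is biased.* A reader might infer this because chance baseline imbalance enters the estimate. Under randomisation the estimate is unbiased, the type I error is kept, and the confidence interval already allows for such imbalance. With 3250 per group, the 95% range of a chance baseline difference is ±1.96 × √(2/3250) = ±0.049 SD. At r = 0.5 only half of that, 0.024 SD, reaches the estimate.
- *Every patient has a baseline score, or nearly every one.* The score is scheduled; its completeness is not stated.
- *The plan ignores baseline WHODAS.* It is summarised, checked for imbalance with possible sensitivity adjustment, and built into the disability endpoint. The section 5 provision partly answers the imbalance worry, but it does not recover precision in the main comparison.

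**Conclusion.** The point holds as one of efficiency. The main WHODAS models omit a prognostic baseline score that the trial schedules, and no other section puts it into the main comparison. The variance forgone is 9% to 49% for r between 0.3 and 0.7. That range is assumed; the loss is zero only if r = 0, which is implausible for one instrument in the same patients. The percentages apply to the linear model on the scale analysed, with r on that scale, and do not carry over directly to the rank-based branch. The power figures are illustrative.

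The change is worth making because it costs almost nothing. The omission does not threaten the primary result or the validity of the secondary one.

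**What to change.** Amend section 8.2 before database lock, as section 13 allows:

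- Model WHODAS at 30 days and at 1 year on centre group, randomised treatment and pre-operative WHODAS. If the outcome is log-transformed, enter the baseline on the log scale too. Report the adjusted mean difference with its 95% CI.
- State a simple rule for missing baseline values, such as mean imputation of the covariate. This does not conflict with section 12, which rules out imputing the follow-up scores.
- Replace the unadjusted Mann-Whitney fallback with a method that keeps baseline and centre group, for example rank ANCOVA with outcome and baseline both ranked, or a proportional odds model. Neither yields a mean difference, so say which estimate will accompany the test.
- List the ten measures in section 8.2.1, so that the threshold for WHODAS is known.

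The cost is a few sentences of SAP text. No new data, visits or patients are needed. Pre-specification also removes discretion over whether to adjust once the data have been seen.
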